5.7.1 Peripheral Blood Markers

[REDACTED]

5.7.1.2 Serum [REDACTED] for Kynurenine and Related Metabolites

Serum [REDACTED] will be collected from all subjects at time points as indicated in [Table 5.6-1](#), [Table 5.6-2](#), and [Table 5.6-3](#).

[REDACTED]
Levels of kynurenine, tryptophan, and related metabolites in serum will be determined by LC-MS analysis. Serum levels will be measured on serum frozen after collection from subjects.
[REDACTED]

5.7.2 *Tissue Markers from Fresh Tumor Biopsies*

[REDACTED] With Amendment 14, all subjects in Parts 1 and 3 (as well as subjects in other parts without archival tissue meeting the requirements above) will be required to undergo mandatory pre-treatment biopsies. All subjects will be required to undergo an on-treatment biopsy at acceptable clinical risk as judged by the investigator. Please notify the BMS Medical Monitor if biopsy on-treatment may pose unacceptable clinical risk, or if tumor at the time of on-treatment biopsy is not accessible for sampling.

An optional specimen (not mandatory) at the time of disease progression or during another clinically meaningful event (eg, response or AE) may be collected.

Where possible, biopsied lesions should be distinct from index lesions being evaluated for radiological response. Biopsies may be excisional, incisional, or core needle. Excisional biopsies are strongly encouraged where feasible. Biopsies from previously irradiated lesions are only suitable if they subsequently progressed. Baseline samples may be obtained at any time following other screening procedures and prior to first dose of study drug (administered on Cycle 0 Day 1 in Part 1 or Cycle 1 Day 1 in Parts 2 and 3). In limited circumstances, recent fresh samples (frozen and FFPE) obtained prior to start of screening that meet biomarker requirements of the study as determined by the Study Director or Medical Monitor may be substituted for fresh biopsies, after permission from the Study Director or Medical Monitor is obtained. Cycle 1 Day 15 specimens may be obtained within a collection window of Cycle 1 Day 15 through Cycle 1 Day 28.

As described previously, complete instructions on the collection, processing, handling, and shipment of all biomarker specimens will be provided in a separate procedure manual. Please refer to this manual for information pertaining to the collection and processing of tissue via biopsy or core needle. Collection procedures at baseline and on-treatment (and at progression) should be completed on a single, appropriately accessible lesion, when applicable. In the case that the lesion sampled at baseline is no longer accessible or within acceptable clinical risk to re-biopsy during study (at Cycle 1 Day 15 or at progression), tissue from alternative lesion(s) may be obtained. This should be documented. Immediate confirmation for presence of viable tumor cells from collected tissue samples is strongly recommended. If adequate tissue is not obtained following initial passages of the needle, repeat passages may be required.

Subjects whose baseline or on-treatment biopsy yields inadequate tissue quantity or quality (lack of tumor) will be allowed to continue in the study [REDACTED]

If tissue obtained from a large proportion of subjects is deemed inadequate for testing (eg, possesses low tumor cell content), additional subjects may be enrolled in an attempt to obtain tissue specimens better-suited for testing.

5.7.2.1 *Tumor Kynurenone and Related Metabolites*

Tumor levels of kynurenone, tryptophan, and related metabolites will be measured in fresh frozen tumor biopsies collected at baseline and on treatment. Kynurenone, tryptophan, and related metabolites will be assessed by LC-MS methods. On-treatment reduction in tumor kynurenone level is the predicted effect of IDO1 inhibition.

5.7.3 *Tissue Markers from Archived Tumor Samples*

Submission of baseline tumor tissue sample is mandatory from all patients. Tumor tissue samples at baseline should be either archival tumor FFPE, FFPE slides and/or fresh biopsy in FFPE block - specified with cohort. One FFPE block of < 1 year old or 20 slides (fewer slides may be acceptable with the approval of the medical monitor, but generally 15 will be required) of less than 4 months old will be requested from patients with no mandatory fresh biopsy requirement at baseline; archival samples from subjects in Parts 1 and 3 are not subject to these time limitations as these subjects will also undergo fresh pretreatment biopsies. These specimens will be submitted for central PD-L1 immunohistochemistry (IHC) in melanoma and NSCLC patients. The pre-treatment tumor samples must be a core biopsy, punch biopsy, excisional biopsy, or surgical specimen. Fine needle aspirates or other cytology specimens are insufficient for enrollment. Tumor samples obtained from bone lesion are not acceptable.

Molecular characterization of archival specimens will be similar to the characterizations described above (IHC [REDACTED]) but are likely to focus on the expression of PD-L1 [REDACTED] as candidate markers associated with response to combination therapy.

Note that HPV status, a known prognostic factor for cervical cancer and SCCHN, will be monitored via CRF. When HPV status is unknown for cervical or SCCHN (oropharyngeal primary location) cancer subjects, HPV status (and type) may be assessed/confirmed retrospectively using archival and/or fresh specimens. Analyses may include p16 IHC and/or HPV detection methods such as, but not limited to, in situ hybridization and PCR-based techniques.

5.8 *Outcomes Research Assessments*

Not applicable.

6 ADVERSE EVENTS

An *AE* is defined as any new untoward medical occurrence or worsening of a pre-existing medical condition in a clinical investigation subject administered study drug and that does not necessarily have a causal relationship with this treatment. An AE can therefore be any unfavorable and unintended sign (such as an abnormal laboratory finding), symptom, or disease temporally associated with the use of study drug, whether or not considered related to the study drug.

The causal relationship to study drug is determined by a physician and should be used to assess all AEs. The causal relationship can be 1 of the following:

- Related: There is a reasonable causal relationship between study drug administration and the AE.
- Not related: There is not a reasonable causal relationship between study drug administration and the AE.

The term “reasonable causal relationship” means there is evidence to suggest a causal relationship.

AEs can be spontaneously reported or elicited during open-ended questioning, examination, or evaluation of a subject. (In order to prevent reporting bias, subjects should not be questioned regarding the specific occurrence of 1 or more AEs.)

6.1 Serious Adverse Events

An *SAE* is any untoward medical occurrence that at any dose:

- results in death
- is life-threatening (defined as an event in which the subject was at risk of death at the time of the event; it does not refer to an event which hypothetically might have caused death if it were more severe)
- requires inpatient hospitalization or causes prolongation of existing hospitalization (see **NOTE** below)
- results in persistent or significant disability/incapacity
- is a congenital anomaly/birth defect

- is an important medical event (defined as a medical event[s] that may not be immediately life-threatening or result in death or hospitalization but, based upon appropriate medical and scientific judgment, may jeopardize the subject or may require intervention [eg, medical, surgical] to prevent 1 of the other serious outcomes listed in the definition above). Examples of such events include, but are not limited to, intensive treatment in an emergency room or at home for allergic bronchospasm, blood dyscrasias or convulsions that do not result in hospitalization). Potential DILI is also considered an important medical event (see [Section 6.7](#) for the definition of potential DILI).

Suspected transmission of an infectious agent (eg, pathogenic or nonpathogenic) via the study drug is an SAE.

Although pregnancy, overdose, cancer, and potential drug DILI are not always serious by regulatory definition, these events must be handled as SAEs (see [Section 6.1.1](#) for reporting pregnancies).

Any component of a study endpoint that is considered related to study drug (eg, death is an endpoint; if death occurred due to anaphylaxis, anaphylaxis must be reported) should be reported as an SAE (see [Section 6.1.1](#) for reporting details).

NOTE:

The following hospitalizations are not considered SAEs in BMS clinical studies:

- a visit to the emergency room or other hospital department < 24 hours, that does not result in admission (unless considered an important medical or life-threatening event)
- elective surgery, planned prior to signing consent
- admissions as per protocol for a planned medical/surgical procedure
- routine health assessment requiring admission for baseline/trending of health status (eg, routine colorectaloscopy)
- medical/surgical admission other than to remedy ill health and planned prior to entry into the study; appropriate documentation is required in these cases
- admission encountered for another life circumstance that carries no bearing on health status and requires no medical/surgical intervention (eg, lack of housing, economic inadequacy, caregiver respite, family circumstances, administrative reason)
- Admission for administration of anticancer therapy in the absence of any other SAEs (applies to oncology protocols)

6.1.1 *Serious Adverse Event Collection and Reporting*

Sections 5.6.1 and 5.6.2 in the IB represent the Reference Safety Information to determine expectedness of SAEs for expedited reporting. Following the subject's written consent to participate in the study, all SAEs, whether related or not related to study drug, must be collected, including those thought to be associated with protocol-specified procedures. All SAEs must be collected that occur during the screening period and within 100 days of discontinuation of dosing and for 30 days post discontinuation of study drug for subjects not receiving combination

therapy. If applicable, SAEs must be collected that relate to any later protocol-specified procedure (eg, a follow-up skin biopsy).

The investigator must report any SAE that occurs after these time periods and that is believed to be related to study drug or protocol-specified procedure.

An SAE report must be completed for any event where doubt exists regarding its seriousness.

If the investigator believes that an SAE is not related to study drug, but is potentially related to the conditions of the study (such as withdrawal of previous therapy or a complication of a study procedure), the relationship must be specified in the narrative section of the SAE Report Form.

SAEs, whether related or not related to study drug, and pregnancies must be reported to BMS or designee within 24 hours of awareness of the event. SAEs must be recorded on the SAE Report Form; pregnancies on a Pregnancy Surveillance Form (electronic or paper forms). The preferred method for SAE data reporting collection is through the electronic case report form (eCRF). The paper SAE/pregnancy surveillance forms are only intended as a back-up option when the eCRF system is not functioning. In this case, the paper forms are to be transmitted via email or confirmed facsimile (fax) transmission to:

SAE Email Address: Refer to Contact Information list.

SAE Facsimile Number: Refer to Contact Information list.

For studies capturing SAEs through electronic data capture (EDC), electronic submission is the required method for reporting. In the event the electronic system is unavailable for transmission, paper forms must be used and submitted immediately. When paper forms are used, the original paper forms are to remain on site

SAE Telephone Contact (required for SAE and pregnancy reporting): Refer to Contact Information list.

If only limited information is initially available, follow-up reports are required. (Note: Follow-up SAE reports must include the same investigator term[s] initially reported.)

If an ongoing SAE changes in its intensity or relationship to study drug or if new information becomes available, the SAE report must be updated and submitted within 24 hours to BMS (or designee) using the same procedure used for transmitting the initial SAE report.

All SAEs must be followed to resolution or stabilization.

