Women of childbearing potential (WOCBP) must not be nursing or pregnant and must be using an acceptable method of contraception. WOCBP must have a negative pregnancy test within 24 hours prior to dosing with study drug.

Study Drug: Includes both investigational [medicinal] products and non-investigational [medicinal] products as listed in [Table 2](#).

Table 2: Study Drugs for CA017003

Medications	Potency	IP/Non-IMP
BMS-986205-04 Capsule	5 mg	IP
BMS-986205-04 Capsule	50 mg	IP
BMS-986205-04 Tablet	25 mg	IP
BMS-986205-04 Tablet	50 mg	IP
BMS-986205-04 Tablet	100 mg	IP
Nivolumab Injection	10 mg/mL (100 mg/vial)	IP
Ipilimumab Injection	5 mg/ml (200 mg/vial)	IP

Abbreviations: IMP = investigational medicinal product; IP = investigational product.

Study Assessments:

- Safety Outcome Measures: Safety assessments will be based on medical review of AE reports and the results of vital sign measurements, ECGs, PEs, and clinical laboratory tests. AEs will be coded using the most current version of Medical Dictionary for Regulatory Activities (MedDRA) and the incidence of observed AEs will be tabulated and reviewed for potential significance and clinical importance. AEs will be assessed continuously during the study and for 100 days after the last dose of nivolumab. Both AEs and laboratory tests will be graded using the NCI CTCAE v4.03.
- Pharmacokinetic Measures: Serial plasma and urinary samples for BMS-986205 [REDACTED] will be collected from all subjects at specified time points during BMS-986205 monotherapy. PK parameters to be assessed following multiple- and single-dose administration are listed in [Section 5.5](#) of the protocol body. Plasma samples of BMS-986205 will be collected during combination treatment. Plasma concentration data will be tabulated using summary statistics.
[REDACTED]

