6b	Melanoma, I-O naïve, PD-L1 negative	40
6c*	BRAF-MT Melanoma, I-O naïve, post BRAFi	8
6d*	BRAF-MT Melanoma, I-O naïve, post BRAFi (nivolumab therapy)	8
6e	Melanoma, prior anti-PD-(L)1	35
6f	Melanoma, prior anti-PD-(L)1 and anti-CTLA-4	37
7	NSCLC	
7a	NSCLC, I-O naïve, PD-L1 positive	40
7b	NSCLC, I-O naïve, PD-L1 negative	40
7c	NSCLC, prior anti-PD-(L)1	35
8	Additional signal-seeking tumors	35
9	Renal cell carcinoma	40

NOTE: The BRAF-mutated, post-BRAF regimen melanoma subjects will be randomized to receive either nivolumab or BMS-986205 + nivolumab.

Abbreviations: BRAFi = BRAF inhibitor; CTLA-4 = cytotoxic T lymphocyte-associated antigen 4; DLBCL = diffuse large B-cell lymphoma; I-O = immuno-oncology; NSCLC = non-small cell lung cancer, PD-1 = programmed cell death-1; PD-L1 = programmed death receptor-ligand 1; PD-(L)1 = either PD-1 or PD-L1; SCCHN = squamous cell carcinoma of the head and neck.

Continuous evaluation of toxicity events in the dose expansions will be performed throughout enrollment in the expansion cohorts. If, at any time, the aggregate rate of treatment-related toxicities meeting DLT criteria exceeds 33% across all subjects treated in the dose expansions, the findings will be discussed and further enrollment may be interrupted. At that time, depending on the nature and grade of the toxicities and after assessing the risk/benefit ratio, a new dose(s) of BMS-986205 for all cohorts may be initiated at a previously tested lower dose level or at a dose level intermediate to previously tested lower dose levels. Additionally, at the discretion of the Sponsor, and in agreement with the investigators, the nivolumab 480 mg Q4W dosing

regimen in the designated expansion cohorts and clinical pharmacology substudy may revert back to 240 mg Q2W based on emerging PK, pharmacodynamic, and/or tolerability data from the cohort expansion portion of the study.

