CBC with Differential and Platelets	X	X	X	X	X	Q2W Nivo dosing only		X	Predose.
LFT Assessments	X	X	X	X	X	Q2W Nivo dosing only		X	Predose; includes AST, ALT, total bilirubin, direct bilirubin (only if total bilirubin is elevated), alkaline phosphatase, and GGT (only when alkaline phosphatase is increased to ≥ Grade 2).

Table 5.1-3: On-treatment Procedural Outline (BMS-986205 + Nivolumab Part 1 Dose Escalation and Part 2 Dose Expansion)

Procedure	Cycle 1 (4 weeks)				Cycles 2+ (4 weeks)			End of Treatment ^{a,b,c}	Notes
	Day 1	Day 8	Day 15	Day 22	Day 1	Day 15 (±2 days)	Day 22 (+7 days) ^d		
Thyroid Function Tests	X				X			X	If collected at screening do not repeat on Cycle 1 Day 1. Collect every 2 cycles, predose, beginning with Cycle 3 Day 1 and at the end of treatment. To include TSH with reflex testing to free T3 and free T4 if TSH abnormal. Results should be examined by the investigator or appropriate designee within 48 hours of dose administration.
Pregnancy Test (WOCBP)	X		Q2W Nivo dosing only		X	Q2W Nivo dosing only		X	Serum or urine pregnancy test must be performed (urine pregnancy test: minimum sensitivity 25 IU/L or equivalent units of hCG) within 24 hours prior to administration of study drug. If pregnancy test is positive, hold all study drugs and perform confirmatory testing. If pregnancy is confirmed, permanently discontinue all study drug and immediately notify Sponsor per Section 6.5 .
Adverse Event Reporting and Concomitant Medication Assessments									
Concomitant Medication Assessments	X	X	X	X	X	Q2W Nivo dosing only	X	X	Review prior to dosing.

Table 5.1-3: On-treatment Procedural Outline (BMS-986205 + Nivolumab Part 1 Dose Escalation and Part 2 Dose Expansion)

Procedure	Cycle 1 (4 weeks)				Cycles 2+ (4 weeks)			End of Treatment ^{a,b,c}	Notes
	Day 1	Day 8	Day 15	Day 22	Day 1	Day 15 (±2 days)	Day 22 (+7 days) ^d		
Monitor for Nonserious Adverse Events	X	X	X	X	X	Q2W Nivo dosing only	X	X	Nonserious AEs will be collected starting with the first dose of study drug and through 100 days after discontinuation of nivolumab.
Monitor for Serious Adverse Events	X	X	X	X	X	Q2W Nivo dosing only	X	X	All SAEs must be collected from the date of subject's written consent until 100 days post discontinuation of nivolumab or subject's participation in the study if the last scheduled visit occurs at a later time. eSAEs should be approved in the BMS EDC tool within 5 business days of entry.
Sample Collection									

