Monitor for Serious Adverse Events	X	X	X			All SAEs must be collected from the date of subject's written consent until 100 days after completion of study drugs (or 30 days if subject only received BMS-986205) or subject's participation in the study if the last scheduled visit occurs at a later time. eSAEs should be approved in the BMS EDC tool within 5 business days of entry.
Concomitant Medication Assessments	X	X	X			
Sample Collection						
Pharmacokinetic Assessments	See Section 5.4					
Immunogenicity (ADA) Assessments	See Section 5.4.					
Efficacy Assessments						
Diagnostic Imaging			X		X	See Section 5.4

Table 5.1-7: Follow-up Procedural Outline (CA017003)

Procedure	Clinical/Safety Follow-up			Survival/Long-term Follow-up All Subjects Begins After Completion of Clinical/Safety Follow-up Every 12 Weeks (\pm 2 weeks) Until 2 years After FIRST Dose of Study Drug and a Minimum of 12 months after LAST Dose of Study Drug^b	Response Follow-up ^c Begins After Completion of Safety Follow-up (\pm2 weeks) Until End of Survival Follow-up	Notes
	FU 1 30 days ^a (\pm 10 days)	FU 2 60 days (\pm 10 days)	FU 3 100 days (\pm 10 days)			
Assessment of Subject Survival Status				X		Subject status will be assessed by either a clinic visit or telephone contact.
New Subsequent Anti-cancer Therapies	X	X	X	X		Any new anti-cancer therapies (including surgery and radiotherapy) will be recorded.

^a Follow-up visits at Days 30, 60, and 100 (\pm 10 days) should occur after the last dose of study drug or should coincide with the date of discontinuation \pm 10 days if date of discontinuation is greater than 30 days after the last dose to monitor for adverse events.

^b Follow up after first dose of combination therapy, not monotherapy lead-in.

^c Only for subjects with CR, PR, or SD at end of treatment.

Abbreviations: ADA = anti-drug antibody; AE = adverse event; ALT = alanine aminotransferase; AST = aspartate aminotransferase; BUN = blood urea nitrogen; CBC = complete blood count; CR = complete response; ECOG = Eastern Cooperative Oncology Group; FU = follow-up; GGT = gamma-glutamyl transferase; hCG = human chorionic gonadotropin; IWG = International Working Group; LDH = lactate dehydrogenase; LFT = liver function test; PR = partial response; RECIST = Response Evaluation Criteria In Solid Tumors; SAE = serious adverse event; TSH = thyroid-stimulating hormone; WOCBP = women of childbearing potential.

Table 5.1-8: Re-treatment Day 0 Procedural Outline (CA017003)

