BMS will provide a BMS-approved protocol and any amendments or administrative letters (if required) and IB. CRFs (electronic or hard copy) will be provided by BMS. BMS/The Central Laboratory will provide labels and tubes for the collection of blood samples for PK/biomarker analysis.

Additionally, the IVRS manual and pharmacy manual will also be provided.

5.3 *Safety Assessments*

AEs will be assessed continuously during the study and for 100 days after the last dose of study drug. AEs will be evaluated according to the NCI CTCAE v4.03 and should be followed per requirements in [Sections 6.1.1](#) and [6.2.1](#). AEs will be coded using the most current version of Medical Dictionary for Regulatory Activities (MedDRA) and reviewed for potential significance and importance. Subjects should be followed until all treatment-related AEs have recovered to baseline or are deemed irreversible by the investigator.

Protocol-specified assessments are detailed in [Section 5.1](#).

5.3.1 *Imaging Assessment for the Study*

Any incidental findings of potential clinical relevance that are not directly associated with the objectives of the protocol should be evaluated and handled by the study investigator as per standard medical/clinical judgment

5.3.2 *Laboratory Test Assessments*

A local laboratory will perform the analyses and will provide reference ranges for these tests. Results of clinical laboratory tests performed up to Day -1 must be available prior to dosing. The following clinical laboratory tests will be performed:

Hematology

Hemoglobin
Hematocrit
Total leukocyte count, including differential
Platelet count
Methemoglobin
Reticulocyte counts and haptoglobin (at baseline and reflex when methemoglobin is elevated)
Ferritin (at Screening)
Glucose 6-Phosphate Dehydrogenase deficiency testing (at screening)

Serum Chemistry

Aspartate aminotransferase	Total Protein
Alanine aminotransferase	Albumin
Total bilirubin	Sodium
Direct bilirubin	Potassium
Alkaline phosphatase	Chloride
Lactate dehydrogenase	Calcium
Creatinine	Phosphorus
Blood urea nitrogen	Magnesium
Uric acid	Creatinine clearance (CrCl)- screening only
Glucose (Fasting at screening only)	Bicarbonate/carbon dioxide
Amylase	
Lipase	
Gamma-glutamyl transferase only when alkaline phosphatase is \geq Grade 2	

Urinalysis (at screening)

Protein
Glucose
Blood
Leukocyte esterase
Specific gravity
pH
Other:
24 hour urine collection for testing of p-chloroaniline

Serology

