The Simon 2-stage design will not be used for the mixed cohort of additional signal-seeking tumor types in Part 2. Approximately 35 to 40 subjects will be enrolled to allow for the exploration of early efficacy signals seen during the dose escalation portion of the trial as well as potential signals arising from ongoing trials of other IDO1 inhibitors in combination with anti-PD-(L)1. A 2-stage design will also not be utilized for the RCC and I-O naïve melanoma and NSCLC cohorts, as nivolumab is already an established standard of care in these settings. Approximately 40 subjects will be enrolled in each of these cohorts to allow for the exploration of early efficacy signals of BMS-986205 in combination with nivolumab.

Approximately 16 melanoma I-O naïve BRAF mutant subjects' post-BRAF inhibitor therapy will be randomized into 2 cohorts and will either be treated with nivolumab or nivolumab in combination with BMS-986205, but will not be used for formal statistical comparison.

Table 8.1.2-1: Dose Expansion: Example of Simon 2-stage Design Characteristics

Expansion Cohort	Historic ORR (%)	Target ORR (%)	Stage 1 /Total N	Stage 1 Responses Futility Boundary	Alpha/Power (%)	Probability of Early Stopping (%)
Cervical, Melanoma: Prior anti-PD-(L)1, Pancreatic NSCLC: Prior anti-PD-(L)1, and DLBCL	10	30	12/35	1	10/90	66
Bladder and SCCHN	25	50	10/27	2	10/90	53
Melanoma: Prior anti-PD-(L)1 and anti-CTLA-4	5	20	12/37	0	10/90	54

*Note: For the melanoma, prior anti-PD-(L)1, and prior anti-PD-(L)-1/anti-CTLA-4 cohorts, the analysis will be focused on approximately 35 subjects who are BRAF (wild-type) WT.

Abbreviations: CTLA-4 = cytotoxic T lymphocyte-associated antigen 4; DLBCL = diffuse large B cell lymphoma; I-O = immuno-oncology; NSCLC = non-small cell lung cancer; PD-1 = programmed cell death; PD-L1 = programmed death receptor-ligand 1; PD-(L)1 = either PD-1 or PD-L1; ORR = objective response rate; SCCHN = squamous cell carcinoma of the head and neck..

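### Section 6.1.1 and the Section 5.1 tables disagree on who has a 30-day SAE window, which by wording catches nivolumab-only cohort 6d, and the 100-day AE clock has no single starting point

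*Combined protocol and SAP*

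**What the plan says.** **Length of the window.** Section 6.1.1 requires SAEs to be collected during screening and "within 100 days of discontinuation of dosing and for 30 days post discontinuation of study drug for subjects not receiving combination" therapy. Table 5.1-7, the follow-up schedule, sets SAE collection "until 100 days after completion of study drugs (or 30 days if subject only received BMS-986205"). Tables 5.1-2, 5.1-13 and 5.1-15 carry the same restriction.

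**The subjects affected.** Section 8.1.2 says that about 16 BRAF-mutant melanoma subjects "will be randomized into 2 cohorts and will either be treated with nivolumab or nivolumab in combination with BMS-986205". Table 3.1.6-1 lists the nivolumab arm as cohort 6d, "BRAF-MT Melanoma, I-O naïve, post BRAFi (nivolumab therapy"), with 8 subjects. Cohort 6c, the combination arm, also has 8.

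**Start of the clock.** The synopsis says "AEs will be assessed continuously during the study and for 100 days after the last dose of nivolumab". Section 5.3 says "AEs will be assessed continuously during the study and for 100 days after the last dose of study drug". Table 5.1-3 says "Nonserious AEs will be collected starting with the first dose of study drug and through 100 days after discontinuation of nivolumab".

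**After the window.** Section 6.1.1 goes on: "The investigator must report any SAE that occurs after these time periods and that is believed to be related to study drug" or to a protocol procedure.

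**The concern.** Incidence of AEs and SAEs is the primary safety measure in Section 8.3.1. Section 8.4.3 tabulates every recorded AE by treatment arm and dose level and fixes no analysis window. The collection rule therefore decides what is counted. If Section 6.1.1 is followed as written, two randomised arms have different routine SAE capture, and even a descriptive comparison of their SAE tables would not be like for like.

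The clock problem reaches further, to every part in which daily BMS-986205 is given with nivolumab. Section 6.2.1 gives a start for nonserious AE collection but no end, so the conflicting statements elsewhere are the only stopping rules. Sites that rely on different pages could stop at different times.

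**Working it through.** The plan has no design figure to reproduce here. The check sets the passages side by side and counts days.

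**1. Window for cohort 6d**

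| Source | 30-day group | 6d | 6c |
|---|---|---|---|
| Section 6.1.1 (SAEs) | not receiving combination therapy | 30 days | 100 days |
| Tables 5.1-2, 5.1-7, 5.1-13, 5.1-15 | only BMS-986205 received | 100 days | 100 days |

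The literal difference under Section 6.1.1 is 100 − 30 = 70 days. It concerns SAEs only; no passage gives 6d a 30-day limit for nonserious AEs.

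**2. Fit with the stated reason for 100 days**

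Section 3.1.3.1 explains 100 days as about 5 nivolumab half-lives. Section 1.4.4.2 gives half-lives of 17 to 25 days (single dose) and 26.7 days (multiple dose).

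- 100 days: 100/25 = 4.0 to 100/17 = 5.9 half-lives; 100/26.7 = 3.7.
- 30 days: 30/25 = 1.2 to 30/17 = 1.8 half-lives; 30/26.7 = 1.1.

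A 30-day window for subjects who took only nivolumab does not fit that rationale. This supports reading the Section 6.1.1 clause as loose wording.

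**3. Where the 100-day clock starts**

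| Start | Places |
|---|---|
| Nivolumab | Synopsis; Tables 5.1-1, 5.1-3 to 5.1-6, 5.1-10 to 5.1-12 |
| Study drug(s) | Section 5.3; Tables 5.1-2, 5.1-7, 5.1-13, 5.1-15 |
| Mixed | Table 5.1-9: study drugs for nonserious AEs, completion of study for SAEs |
| Dosing | Section 6.1.1 |

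The 30-day limit in Table 5.1-14 concerns BMS-986205 monotherapy in the QTc substudy and is not part of the conflict.

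**4. How far the two main clocks can separate**

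Gap = day of last BMS-986205 dose − day of last nivolumab dose, in a completed cycle with daily BMS-986205 to its last day. The nivolumab-anchored window then closes (100 − gap) days after the last BMS-986205 dose.

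| Nivolumab schedule | Last nivolumab | Last BMS-986205 | Gap | Window closes |
|---|---|---|---|---|
| Q4W, 4-week cycle | Day 1 | Day 28 | 27 days | Day 73 |
| Q3W, 6-week cycle | Day 22 | Day 42 | 20 days | Day 80 |
| Q2W, 4-week cycle | Day 15 | Day 28 | 13 days | Day 87 |

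The gap does not arise in cohort 6d, where nivolumab is the only study drug.

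**5. Which events depend on the choice of clock**

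The nivolumab-anchored SAE rows extend collection to the end of participation if the last scheduled visit falls later. Table 5.1-7 times the third follow-up visit at 100 days after the last dose of study drug, so SAE collection reaches that visit under either clock. The nonserious AE rows have no such extension. For them the on-treatment and follow-up tables give different end dates.

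**The case against.** The strongest reply is that this is a drafting slip with little practical effect. Section 6.1.1 never names cohort 6d. The protocol has an obvious 30-day group, subjects who stop during the BMS-986205 lead-in, and four tables describe exactly that group. Section 3.1.3.1 requires at least 100 days of follow-up and three safety visits for all subjects except those who withdraw consent. Table 5.1-7 marks both SAE and nonserious AE monitoring at the Day 100 visit. Related SAEs must be reported whenever they occur. The two arms have about 8 subjects each, Section 8.1.2 rules out formal comparison, and Section 1.1.5.1 justifies the nivolumab arm by a lack of efficacy data, not safety data.

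Most of this stands, and it limits the size of the problem. It does not remove the contradiction: Section 6.1.1 is the section that governs SAE collection, and its words cover 6d.

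A reader might infer three stronger things that the documents do not support.

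- **That 6d would record about 30% as many post-treatment SAEs as 6c (30/100) and so look safer.** This needs a constant post-treatment SAE hazard, which the documents do not give. It also ignores the duty to report related SAEs late and the Day 100 visit.
- **That nonserious AEs in the last weeks go uncollected.** Table 5.1-7 schedules their collection at Day 100. What is uncertain is which rule a site follows.
- **That the clock gap cuts SAE collection short.** The SAE rows run to the last scheduled visit.

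**Conclusion.** The contradiction is real, lies in current operative text, and should be corrected. Followed literally, Section 6.1.1 gives randomised cohorts 6d and 6c routine SAE windows of 30 and 100 days. The exposure is mainly SAEs judged unrelated, with onset on Days 31 to 100, in about 8 subjects. No direction-and-size estimate of bias can be derived from the documents.

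The inconsistent clock is broader but also modest. The two main anchors can differ by up to 27, 20 or 13 days for Q4W, Q3W and Q2W nivolumab, and this bears mainly on nonserious AEs. Those figures assume a completed cycle with BMS-986205 taken to its last day. They could be larger where BMS-986205 continues while nivolumab is delayed for reasons other than toxicity, which Section 4.5.4 provides for. The Table 5.1-9 SAE entry is a separate inconsistency of the same kind.

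**What to change.** Use the rule already in Table 5.1-7 throughout: AEs and SAEs collected to 100 days after completion of study drugs, and to 30 days only if the subject received no study drug other than BMS-986205.

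- In Section 6.1.1, replace the reference to subjects not receiving combination therapy with that condition, so that cohort 6d clearly has 100 days.
- In the synopsis and Tables 5.1-1, 5.1-3 to 5.1-6 and 5.1-10 to 5.1-12, change the anchor from nivolumab to study drugs.
- In Table 5.1-9, change the SAE anchor from completion of study to completion of study drugs.
- Check that Section 5.3 and the remaining Section 5.1 tables carry the same rule, including the 30-day exception.

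The cost is wording only. The Day 100 visit is already timed from the last dose of study drug, so no visit is added. The nonserious AE window becomes slightly longer under the tables now anchored on nivolumab, by up to 27 days in a completed Q4W cycle.
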